these data we predict that suvorexant will not precipitate REM sleep-related parasomnias in the proposed target population but rather will consolidate fragmented REM sleep periods that have been observed in the earlier stages of PTSD. This would be similar to the effects seen for the alpha 1 adrenergic antagonist prazosin, an agent that targets central noradrenergic arousal promoting mechanisms and has been shown to reduce the severity of nightmares and related sleep disruption with PTSD. Specifically, the only study that monitored EEG sleep found lengthened discreet REM sleep periods with increases in the amount of REM sleep that were proportionate to the increases in overall sleep time. Prazosin, however, did not reduce time to fall asleep in this study.²⁴ Given the data from animals and that the absence of changes was in healthy volunteers, we hypothesize that suvorexant will also enhance SWS when it is deficient at baseline.

Summary of Significance

Insomnia is quite common among those exposed to trauma. PTSD usually features insomnia symptoms and insomnia precipitated or exacerbated by trauma is also common absent a PTSD diagnosis. TRI does not appear to respond well to previously available treatments. Fragmented patterns of REM sleep have been observed during the development of PTSD and within several years of its onset. Suvorexant is promising for maintaining overall sleep and REM sleep that is being disrupted by heightened arousal. In addition to proposing a placebo-controlled evaluation of efficacy and tolerability of suvorexant for TRI we further propose utilizing PSG to potentially elucidate physiological biomarkers of treatment response. Given the rising toll of trauma this proposal is a timely response to Merck's call for proposals for "clinical studies exploring the investigational use of suvorexant in key insomnia subpopulations."

2.3 Study Design	A double-blind placebo-controlled 6-week trial of suvorexant 10 – 20mg for trauma related insomnia (with and without PTSD) with polysomnography								
-------------------------	---	--	--	--	--	--	--	--	--

2.4 Study Flowchart	(Visits)	Prescreen	Screen	Baseline	Med Week 1	Med Week 2	Med Week 3	Med Week 6	Post-Rx Week1
	Phone screen	X							
	Physical		X						
	Wt. & Vital Signs		X		X	X	X	X	X
	DSISSD and SCID		X						
	LEC		X						
	CAPS			X			X	X	
	ISI			X			X	X	X
	Sleep Diaries			X (1 week)	X		X	X	X(1week)
	PSG			XX			X		
	AE				X	X	X	X	X

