
2.5 Study Procedures
	
Participants
 
Recruitment:
 
We will recruit 90 adults with the expectation of retaining 70 (see power analysis). Participants will be between the ages of 18 to 55 with insomnia and trauma exposure (see below). Recruitment will occur over a 2 1/2 year period with the expectation of recruiting 3 per month and having 2 months for start-up and 6 months for final data analysis and preparing presentations and manuscripts. We will utilize advertisements including 10 radio and 10 newspaper ads in the Washington Post Express at early and other strategic times during study recruitment. We will also continue to employ recruitment methods that have been successful for our program in recruiting participants with trauma-related symptoms including posting flyers on the Howard University campus and in strategic locations in the Washington DC community, and referrals from prior participants. Those who meet initial criteria by phone or on-site screening will be invited to the Clinical Research Unit (CRU) for further screening and informed consent. We will recruit men and women. This study will be open to all ethnic and racial groups; however, with the study location of Howard University in urban DC we anticipate that many of the recruited participants will be from minority groups.
 
Screening Procedures:
 
Participants will initially be screened over the phone with a preliminary checklist of inclusion and exclusion criteria as well as be further informed regarding the purpose and goals for the study. Those who remain interested and appear to meet study criteria will be invited for the screening evaluation at the Howard University CRU. (See study flow chart.)
 
Inclusion criteria and justification:
 
Physically healthy young to middle-aged adults (age 18-55) who report on screening and are confirmed by a clinical interview to meet the Diagnostic and Statistical Manual of Mental Disorders – 5th Edition (DSM-5) criteria for primary insomnia and Criterion A (exposure to a traumatic event) for PTSD.²⁵ Insomnia symptoms must have started or worsened after the exposure to the index trauma. We anticipate that approximately half of the recruited sample will meet criteria for PTSD thus enabling comparisons between those with TRI present or absent PTSD.
 
Exclusion criteria:
 
 1. Psychiatric disorders other than insomnia, PTSD and specific phobias; including bipolar and psychotic disorders and meeting criteria for DSM-5 moderate alcohol or drug use disorders within the past year. 2. Diagnosis of a sleep disorder other than insomnia including PSG findings of apnea/hypopnea or periodic limb movement indices > 10/hour;

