------------------------------------	---

- 3. Consistent (daily) use of medication other than medications taken for blood pressure or nonnarcotic medications for pain and/or inflammation, or medical conditions that compromise sleep;
- 4. Caffeine use exceeding 5 cups of coffee per day or its equivalent;
- 5. Habitual bedtimes after 3AM, habitual rise times after 10AM, or habitual napping > 1hour/day;
- 6. Pregnancy or breastfeeding, or expecting to conceive while in study (sexually active women will be required to use a medically acceptable form of birth control);
- 7. Positive urine toxicology.

Procedures

Medication:

After the baseline screening, participants will be randomly assigned to either the suvorexant or placebo group, and suvorexant or placebo will be administered to be taken one hour before bedtime. Randomization will be stratified for the presence or absence of PTSD (full or subthreshold) and gender. Medication will be managed by the research pharmacy and provided to the participant by CRU nursing staff with instructions for use. In case of a missed appointment they will receive a 15 day supply except for between treatment week 3 and week 6 when they will receive a 4 week supply. Initial dosing will be 10 mg. At week one, [name] or a study clinician in consultation with [name], will determine whether to increase to 20 mg. based on tolerance of the medication and persistence of symptoms. If there are no, or only negligible, side effects and insomnia symptoms remain present then the dose will be increased. If tolerability is compromised by the dose increase the study clinician will have the option of reducing back to 10 mg if done at or before the week 2 study visit. Dose increases can be deferred until week 2 but after this visit medication dose will be held constant until the end of the study. Participants will discontinue medication after the week 6 study visit. At the final follow-up 1 week later clinical assessment will inform the study clinician's recommendation for further treatment including possible resumption or initiation of suvorexant. At each medication study the coordinator or research nurse will conduct a pill count and review diaries to determine adherence. They will also query for potential adverse events including a list of the most common adverse effects reported in the suvorexant trials^{22,23} will be queried as well as any events suggestive of parasomnias or narcolepsy phenomena (see Assessments below).

Assessments:

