The following diagnostic and outcome assessments will be performed by research staff members blind to participants' treatment condition.

	
(Diagnostic)
 
Duke Structured Interview Schedule for DSM-IV-TR and International Classification of Sleep Disorders 2nd edition (ICSD-2) Sleep Disorder Diagnoses (DSISSD)²⁶ – A widely used semi-structured interview designed to assess sleep disorder diagnostic status. We will use this interview to evaluate the presence of insomnia and to rule out insomnia that is accounted for by a mental disorder other than PTSD, medical conditions, and substance use, parasomnias, narcolepsy, and circadian rhythm sleep disorders. This interview will establish the onset and course of insomnia, with in conjunction with the information from the LEC and CAPS (see below) will determine the criteria for “trauma-related.”
 
Structured Clinical Interview for DSM-V (SCID)²⁷ The SCID is semi-structured diagnostic interview that assesses the DSM diagnostic criteria for psychiatric disorders and is considered the “gold standard” for assessing mental disorders. A modification will be utilized in order to screen for excluded and establish allowable comorbid conditions.
 
Life Event Checklist (LEC),²⁸ is an inventory of lifetime exposure to traumatic events that lists 15 of the more common categories of trauma experiences and asks for endorsement of whether they occurred directly to the person or were witnessed and the age of exposure.
 
The Clinician Administered PTSD Scale (CAPS)²⁹ will be administered to further assess the details of trauma exposure, and (past week) PTSD severity, and lifetime diagnostic criteria. The CAPS evaluates the frequency and intensity of each of the 17 symptoms of PTSD and is considered a gold standard for assessment of the diagnosis and severity of PTSD.
 
(Assessments used for outcomes)
 
Insomnia Severity Index (ISI)³⁰ The ISI is a seven-item measure used to evaluate insomnia severity for the past two weeks. Items are scored on a 5-point scale and a total score is obtained by summing the seven items, with higher scores indicating greater insomnia severity. A cutoff score of 10 has been determined to be optimal for detecting insomnia in population samples. The ISI is also validated as an outcome measure for insomnia treatment studies and is widely used for that purpose.
 
Sleep diary - Participants will complete our standard sleep diary each morning throughout this trial. The diary includes questions about bedtime, final awakening time, sleep onset latency (SOL) estimate, the number of awakenings, and duration of each awakening, overall sleep satisfaction, morning restfulness, adherence/non-adherence to the study medication regimen, nightmare frequency, and content of nightmare. Estimated total sleep time (TST) and wake after sleep onset (WASO) for each night will be calculated using information provided in the diary.
 
One week CAPS nightmare item and total score minus sleep items.

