--	--

Adverse Event Screening At each medication visit participants will be queried regarding the presence of any new symptoms or concerns. We will specifically query the adverse effects that occurred at a frequency that exceeded placebo in either the 3 month pivotal trials²² or the 1-year study²³ including somnolence, fatigue, dry mouth, dyspepsia, and peripheral edema. We will also specifically query the pre-specified events of interest for those trials including suicidal ideation, complex sleep-related behaviors (e.g. getting food during the night and not remembering it), sleep onset or off-set hallucinations, sleep paralysis, and falls. Excessive daytime sleepiness will be assessed by administering the Epworth Sleepiness Questionnaire.³¹ Weight and vital signs will be obtained at each study visit. At the post-treatment visit specific inquiry will also include the occurrence of common medication withdrawal symptoms such as dizziness, shaking, nausea, and muscle tension as well as re-assessment of insomnia and sleep patterns for that period.

Polysomnography (PSG):

PSG collection includes a standard electroencephalogram (EEG) montage with two central, frontal, and occipital leads, two electrooculograms, chin and limb electromyograms, and an electrocardiogram (ECG). Recordings will be conducted using an Embla (Denver, CO) Titanium unit in the CRU. Screening for sleep disordered breathing and limb movements will be performed using the screening night data. Visual scoring of sleep records from a computer monitor will be done following the American Academy of Sleep Medicine (AASM) Manual, Version 2.0.³² The REMLogic software (Embla) will calculate sleep parameters including TST, SOL, WASO, the percentage of each sleep stage, and mean duration of continuous REM segment. Calculation of REM segment length used our previous criteria¹⁶ of at least two epochs of consecutive REM sleep with no more than one 30-sec epoch of non-REM sleep interruption. The sleep parameters for baseline will be obtained from the second night recording after an accommodation recording that will also screen for apnea will be used in data analysis. Respiratory strain gauge, nasal air flow, and oximetry monitors will be included on the first but not subsequent nights. Participants will be instructed to go to bed near their habitual bedtimes and will wake up naturally. PSG will be done prior to medication and after 3 weeks of medication treatment to allow for stable dosing.

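### No pre-dose adverse-event checklist is scheduled and the Epworth has no stated visit, so whether a symptom is new in a given participant rests on recall and change in sleepiness cannot be computed

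*Combined protocol and SAP*

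**What the plan says.** **Timing of the AE query.** Section 2.5, Adverse Event Screening: "At each medication visit participants will be queried regarding the presence of any new symptoms or concerns". In the table headed "2.4 Study Flowchart", the AE row is blank at Prescreen, Screen and Baseline. It is marked at medication weeks 1, 2, 3 and 6 and at the post-treatment week.

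**Content of the query.** Besides the open question, staff prompt for effects seen more often than on placebo in the suvorexant trials, such as somnolence and fatigue. The plan continues: "We will also specifically query the pre-specified events of interest for those trials including suicidal ideation, complex sleep-related behaviors". The list goes on to hallucinations around sleep, sleep paralysis and falls.

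**Epworth.** It is named once, in the same paragraph: "Excessive daytime sleepiness will be assessed by administering the Epworth Sleepiness Questionnaire". No visit is given there, and the flowchart has no row for it.

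**What is recorded before treatment.** The sleep-disorder interview (DSISSD) at Screen is used to rule out insomnia due to other causes and other sleep disorders, including "medical conditions, and substance use, parasomnias, narcolepsy, and circadian rhythm sleep disorders". For the SCID, "A modification will be utilized in order to screen for excluded and establish allowable comorbid conditions". The exclusions include "Psychiatric disorders other than insomnia, PTSD and specific phobias; including bipolar and psychotic disorders". The ISI, CAPS, sleep diary and PSG all have a Baseline mark.

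**Analysis.** Tolerability is part of Objective 2 and is the subject of Hypothesis 2c. Section 2.7 plans AE frequencies, set descriptively against the published suvorexant insomnia trials. It states no AE or Epworth comparison between arms.

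**The concern.** Several prompted items are complaints that people with insomnia, about half of whom are expected to have PTSD, may well bring into the trial: sleepiness, fatigue, sleep-related hallucinations, suicidal ideation. If these are asked about for the first time after dosing starts, a positive answer at week 1 cannot be checked against a recorded starting state. The Epworth is a score and shows change only against an earlier value.

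At stake is the tolerability objective. Each participant's treatment-emergent status would depend on memory. Event rates would mix new symptoms with old ones by an unknown amount, and those rates are what the plan sets beside the external trials. Side effects also enter the week 1 dosing decision described in section 2.5, again without a recorded baseline. A missing pre-dose measurement cannot be recovered once treatment has begun.

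**Working it through.** The plan states no figure on this point, so there is none to reproduce. The check has two parts: reading the schedule, then an illustration of size.

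**1. Schedule.** The flowchart and the text agree that AE queries begin at medication week 1. The Epworth is absent from the flowchart and undated in the text. The efficacy measures have a Baseline mark; the tolerability checklist and the Epworth do not. The Screen interviews establish diagnoses. No item-level symptom record is stated for them, and someone with sub-diagnostic sleepiness or isolated sleep paralysis could pass screening with nothing on file.

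**2. Effect on event rates.** Inputs from the documents: somnolence 7% on suvorexant and 4% on placebo (section 2.2); 70 participants retained (section 2.5). Assumptions: 1:1 allocation, so n = 70/2 = 35 per arm; and q, the share in each arm whose pre-existing symptom is counted as an event. The documents give no q, so a range is shown.

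Observed rate = q + (1 − q)p. Half-width of the 95% interval for the difference = 1.96 × √[a(1 − a)/35 + b(1 − b)/35], where a and b are the observed rates.

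| q | suvorexant | placebo | difference (points) | half-width (points) |
|---|---|---|---|---|
| 0 | 7.0% | 4.0% | 3.0 | 10.7 |
| 0.1 | 16.3% | 13.6% | 2.7 | 16.7 |
| 0.2 | 25.6% | 23.2% | 2.4 | 20.1 |
| 0.3 | 34.9% | 32.8% | 2.1 | 22.2 |

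For example, at q = 0.2 the suvorexant rate is 0.2 + 0.8 × 0.07 = 0.256. The inflation is q(1 − p) = 0.2 × 0.93 = 18.6 points. Both arms rise almost equally, so the difference between arms shrinks slightly and becomes less precise, and no false drug effect appears. The absolute rate changes a great deal, and the absolute rate is what an external contrast uses.

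**3. Epworth precision.** Assumptions: 35 per arm, two-sided 0.05, 80% power, and a baseline-to-follow-up correlation r that the documents do not give. Adjusting for baseline multiplies the variance by 1 − r². The detectable standardised difference is (1.96 + 0.84) × √[(2/35)(1 − r²)].

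| r | 1 − r² | detectable d |
|---|---|---|
| no baseline | 1 | 0.67 |
| 0.3 | 0.91 | 0.64 |
| 0.5 | 0.75 | 0.58 |
| 0.7 | 0.51 | 0.48 |
| 0.8 | 0.36 | 0.40 |

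**The case against.** The strongest reply is that the trial is randomised and double-blind: "participants will be randomly assigned to either the suvorexant or placebo group". Pre-existing symptoms are therefore balanced in expectation. A reader might infer from the missing baseline that prior symptoms cannot be told apart from drug effects at all. The documents do not support that, because the placebo arm separates the two at group level. This part of the objection stands in full.

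A reader might also infer that treatment-emergent events cannot be defined. That too goes beyond the text. The open question asks about new symptoms, which is a treatment-emergent criterion, though one that relies on recall. The word is not attached to the prompted items or to the Epworth.

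The starting state is not wholly unknown. The DSISSD, the SCID, the psychiatric and sleep-disorder exclusions, the limit on habitual napping and a one-week baseline diary all give some information and probably lower the prevalence of the prompted symptoms. They do not supply an item-level record.

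The flowchart is also incomplete in other respects: it has no row for urine toxicology or pill counts. The missing Epworth row therefore does not prove that no baseline Epworth is intended. The exact defect is that its timing is unspecified, during treatment as well as before it.

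Finally, the size is hypothetical. It is tempting to say that a baseline Epworth is worth 33% to 96% more participants (1/0.75 to 1/0.51), but that takes r as 0.5 to 0.7 without a source and applies to a comparison the plan does not specify. Nor would baseline data make the somnolence comparison informative: power for 7% against 4% with 35 per arm is about 8% two-sided even with no dilution. Nor do the documents say how the external trials handled baseline symptoms. Those trials do have a placebo rate, so the external contrast could be referenced to placebo.

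**Conclusion.** The point holds in a limited form. Following the plan as written, no AE checklist is given before the first dose and the Epworth belongs to no visit. Per-participant treatment-emergent status then rests on recall, and change in sleepiness cannot be computed unless a baseline Epworth is added. The placebo arm supports an unbiased but less precise group comparison, which section 2.7 does not specify. The stated external contrast is the most exposed part: over the assumed range of q from 0.1 to 0.3, a 7% rate would read as 16.3% to 34.9%.

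These figures are illustrative. They rest on 1:1 allocation, 35 per arm, and a prevalence and a correlation that the documents do not give. No efficacy hypothesis, alpha level or sample size is affected. The change is still worth making because it costs little, serves a named objective, and cannot be made for a participant after the first dose.

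**What to change.** - Give the same AE checklist and the Epworth at the existing Baseline visit, before the first dose.
- Add an Epworth row to the flowchart in section 2.4 marking every visit at which it is given, and add a Baseline mark to the AE row.
- State in section 2.7 that only events new or worse than baseline count as treatment-emergent, and tabulate them by arm alongside the external contrast.
- Compare the Epworth between arms, adjusted for its baseline value. Label any expected gain in precision (variance factor 1 − r²) as illustrative.

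**Cost:** a few minutes of questionnaires per participant at a visit that already takes place, plus short edits to the flowchart and the analysis section. No extra visit, procedure or staff is needed.

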2.7 Statistical Analysis and Sample Size Justification	
The data will be analyzed by the Investigator and Co-investigator.
 
Main outcomes will be ISI, CAPS nightmare frequency and total score, diary and PSG sleep latency and WASO at week 3 and for non-PSG variables Med week 6. We will also explore effects on REM and SWS and their relationships to other study outcomes.
 
An alpha level of .05 (one-tailed) will be applied in testing Hypotheses 2a), 2b), 2d), and 2e). Initially, data will be pre-screened for errors, outliers, normality of distributions, and any necessary modifications, such as transformation of variables and/or elimination of cases, will be conducted.
 
Our initial objectives are descriptive. We will generate frequencies of types of trauma exposures associated with insomnia and the rates for PTSD diagnoses and sub-diagnostic threshold PTSD symptoms in the recruited study population (Objective 1) and the frequency of adverse events (Objective 2). The latter will be descriptively contrasted to the extant data for suvorexant from the insomnia registry trials as a guide to planning future trials including dosing.
 
Hypothesis 2a) Insomnia will improve, and nightmares and other PTSD symptoms will be reduced with suvorexant treatment compared with placebo: We will compare baseline characteristics of the treatment groups using independent samples t-tests for continuous variables or chi-square tests for categorical variables. If a significant group difference is found in some of the variables, the variable(s) will be included in subsequent analyses as a covariate(s). We will perform 2 (Group) x 3 (Time: baseline, Med week 3, and week 6) mixed ANOVAs or ANCOVAs [if there is a covariate(s)] to compare the changes in ISI scores, nightmare frequency, and CAPS scores, separately, between the two groups.
 
Hypothesis 2b) Improved sleep will be associated with reduced non-sleep PTSD symptoms: Correlation coefficients between baseline – Med week 6 changes in sleep measures (e.g., ISI scores and nightmare frequency) and changes in the CAPS scores excluding two sleep-related items will be computed. In addition, we will exploratively examine if there is an interaction with treatment condition by performing regression analyses in which CAPS scores will be predicted by changes in sleep measures, treatment condition, and a Sleep measure X Treatment condition interaction.
 
Hypothesis 2d) Sleep latency and wake after sleep onset (WASO) will be reduced with suvorexant treatment compared with placebo: We will perform 2 (Group: suvorexant vs. placebo) x 2 (Time: Baseline and Med week 3) mixed ANOVAs or ANCOVAs [if there is a covariate(s)] to compare the changes in PSG measured sleep latency and WASO between the suvorexant and placebo groups.
 
Exploratory hypothesis 2e) When reduced at baseline (i.e., SWS below 100 minutes and mean REM segment duration below 15

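### The four withdrawal symptoms are asked about by name only after medication has stopped, so no prompted on-drug value exists to separate background symptoms from symptoms that appear on stopping.

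*Combined protocol and SAP*

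**What the plan says.** Adverse Event Screening in section 2.5 sets out three layers of questioning.

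- **Open question.** "At each medication visit participants will be queried regarding the presence of any new symptoms or concerns".
- **Two prompted lists at medication visits.** The first covers effects that were more frequent than on placebo in the cited suvorexant trials, "including somnolence, fatigue, dry mouth, dyspepsia, and peripheral edema". The second covers the events of interest from those trials: "suicidal ideation, complex sleep-related behaviors (e.g. getting food during the night and not remembering it), sleep onset or off-set hallucinations, sleep paralysis, and falls".
- **An addition at the post-treatment visit.** "At the post-treatment visit specific inquiry will also include the occurrence of common medication withdrawal symptoms such as dizziness, shaking, nausea, and muscle tension".

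On timing, the Medication paragraph of section 2.5 says: "Participants will discontinue medication after the week 6 study visit". The flowchart (section 2.4) marks adverse event screening at Med Weeks 1, 2, 3 and 6 and at Post-Rx Week 1, but not at Baseline.

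On analysis, section 2.7 plans to describe "the frequency of adverse events (Objective 2") and to set those frequencies beside existing suvorexant data from the insomnia trials, as a guide to future trials and dosing. It states no comparison of adverse events between the randomised arms. It does not define a withdrawal symptom.

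**The concern.** A withdrawal symptom is one that appears or worsens when the drug is stopped, so identifying one needs a reference value taken while the participant is still on drug. Here the way of asking changes at the same point as the treatment: an open question before stopping, a named prompt afterwards. The post-treatment prompt asks whether the symptom occurs, not whether it is new or worse. The open question on treatment asks about new symptoms, so by its wording it tends to pass over long-standing ones.

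Muscle tension, dizziness and nausea are non-specific and plausible as background complaints in a trauma-exposed insomnia sample. Tolerability is Hypothesis 2c and part of Objective 2, and the adverse event frequencies are meant to inform later trials. A post-treatment frequency that mixes background with new symptoms is a poor guide for that purpose. A week 6 value that was never asked for cannot be recovered afterwards.

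**Working it through.** The plan gives no withdrawal rate, background rate or threshold, so there is no figure to reproduce. The check is a comparison of the passages, followed by two illustrations.

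**Step 1: where each symptom is named.**

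| Symptom | Medication-visit lists (2.5) | Post-treatment visit (2.5) |
|---|---|---|
| Dizziness | not named | named |
| Shaking | not named | named |
| Nausea | not named | named |
| Muscle tension | not named | named |

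The Baseline column of the flowchart has no adverse event entry. As written, then, neither a pre-drug nor an end-of-treatment prompted value is planned for any of the four.

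**Step 2: effect of changing the question.** Let *p* be the share of participants with at least one of the four symptoms as background, and *s* the share of those whom the open question would pick up. Assume the named prompt picks up all of them and that stopping has no true effect. The apparent rise within an arm from on-treatment to post-treatment is then

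rise = *p* − *p* × *s* = *p*(1 − *s*).

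Both *p* and *s* are assumptions. Section 2.5 expects 70 retained; equal allocation, also assumed, gives 70 / 2 = 35 per arm.

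| *p* | Rise at *s* = 0.75 | Rise at *s* = 0.25 | Participants of 35 |
|---|---|---|---|
| 5% | 1.25 points | 3.75 points | 0.44 to 1.31 |
| 10% | 2.5 points | 7.5 points | 0.88 to 2.63 |
| 20% | 5 points | 15 points | 1.75 to 5.25 |
| 30% | 7.5 points | 22.5 points | 2.63 to 7.88 |

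If the open question captures everything (*s* = 1), or there are no background symptoms (*p* = 0), the rise is zero. The same rise is expected on placebo, so the expected between-arm difference is 0.

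**Step 3: what a week 6 reference removes.** Assume that 20–40% endorse at least one item when prompted, whatever the treatment, and that 60–80% of these would also have endorsed it at week 6. With no drug effect:

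- Post-treatment value only: 0.20 × 35 = 7 to 0.40 × 35 = 14 participants.
- New since week 6: 35 × 0.20 × (1 − 0.80) = 1.4 to 35 × 0.40 × (1 − 0.60) = 5.6 participants.

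The second line counts new endorsements only. A background symptom that happened to worsen would add to it under a new-or-worse rule.

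**Step 4: precision of the placebo contrast.** With 35 per arm and the same rate *p* in both arms, the standard error of the difference is √(2*p*(1 − *p*)/35). At *p* = 20% this is √(0.32/35) = 0.096, a 95% half-width of 1.96 × 0.096, or about 19 points. The contrast is unbiased but wide.

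**The case against.** The strongest reply is that the design already contains the right control. Section 2.5 says "participants will be randomly assigned to either the suvorexant or placebo group". Stopping after week 6 and the post-treatment inquiry are both worded without distinction by arm, and section 2.5 says of the assessments: "The following diagnostic and outcome assessments will be performed by research staff members blind to participants' treatment condition". Background symptoms and any effect of prompting should therefore fall equally on both arms. This stands: a between-arm comparison at Post-Rx Week 1 would not be biased by the prompt. What it leaves open is that section 2.7 commits to no such comparison and names only external trials as the reference. Randomisation does not protect that contrast.

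A second reply is that the symptoms can be recorded during treatment. The open question runs at every medication visit, and the first prompted list is introduced as including five effects, so it may not be exhaustive. Whether dizziness or nausea met its rule depends on cited trials that cannot be consulted here. This also stands in part: that the four items are prompted only after stopping is the plain reading, not a certainty.

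Two stronger readings are tempting, and the documents do not support either:

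- A reader might infer that the rate of these symptoms must rise at the post-treatment visit. It need not. The rise depends on how much the open question captures, which the documents do not give.
- A reader might infer that the plan treats every symptom endorsed at that visit as a withdrawal effect. It contains no counting or attribution rule. The gap is that background and withdrawal cannot be distinguished, not that a misclassification is planned.

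Finally, section 2.7 assigns its alpha level to Hypotheses 2a, 2b, 2d and 2e, not to 2c. No withdrawal test is planned, so power for one is not at issue.

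**Conclusion.** The point holds as a minor weakness in safety data collection. On the plain reading of section 2.5, the four symptoms have no prompted value while participants are on medication. Neither a within-arm reading nor the external contrast in section 2.7 can then separate background symptoms from those that appear on stopping. The placebo arm could supply an unbiased, if imprecise, comparison, but the plan does not say it will be used.

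The size is not known. The 7–14 of 35, against 1.4–5.6 counting only new endorsements, is an illustration. It rests on assumed background and persistence rates and an assumed 35 per arm; only the 70 retained comes from the protocol. No main outcome, hypothesis test or sample size is affected. The case for acting is correct attribution at very low cost.

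**What to change.** In section 2.5, ask the same four items by name at the week 6 visit, before medication is stopped, and again at Post-Rx Week 1. Use the same wording and recall period at both visits, with a simple severity grade so that worsening can be judged. In section 2.7, state that only items new or worse since week 6 are reported as possible withdrawal symptoms, tabulated by randomised arm.

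The cost is four graded questions at a visit where adverse event screening is already scheduled, plus a sentence in each section. The one downside is that prompting at week 6 may slightly raise on-treatment reports of these items, equally in both arms. No dose, schedule or clinical rule changes.
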